# 10.4 Interim Analysis:

The likely hood of observing a statistically significant beneficial treatment effect is dependent on the event rate in the trial. When approximately 1/3 of the subjects have completed one year of follow-up this event rate will be discussed by the SC in order to decide, if the study should continue as planned.

The SC has the right to increase sample size or prolong follow-up if needed.

# 10.5 Access to Individual Subject Treatment Assignments:

Individual subject treatment assignments will be given to the SC if requested. Un-blinded (presented as group A and B) results, including aggregate and subject level data, can be presented to the SC for safety data reviews.

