#### 10.3 Sample Size Considerations:

We expect that 30% of the participants will have documented AF episodes lasting ≥6 minutes (and per protocol qualifying for OAC) during ILR monitoring for at least three years. The study population is expected to have a stroke rate of 0.7%/year in non-AF patients, and 2%/year in AF patients not treated with OAC. While we expect the number of AF-related strokes to be reduced by OAC, we assume that strokes unrelated to AF will not be influenced by this. We also include the assumption that 3% of all participants in the control group will become diagnosed with AF and start OAC. The annual rate of the primary end point in the control group is thus expected to be 1%. Finally, we expect that 5% in the ILR group will not be monitored due to refusal of ILR implantation or ILR explantation due to discomfort. These patients will participate at the same risk as patients in the control group and will be included in the analysis of the primary endpoint according to the intention-to-treat principle. We thus expect the overall hazard ratio to be 0.65. To analyse this reduction in the primary endpoint with a 2-sided α-level of 0.05 and a power of 80% in a 1:3 intervention:control-randomized population, we will need 279 primary events. Follow-up duration will be adjusted to accommodate the number of primary events. With an assumed length of inclusion period of 1-2 years and a median follow-up up 4 years, 6000 subjects will be needed.

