# 10.7 Study Oversight:

# 10.7.1 Steering Committee:

A SC comprising experts in the cardiovascular field will provide oversight and advice to ensure the most safe and efficient conduct and execution of the trial. The SC will consist of external physicians with experience and expertise in the design and conduct of cardiovascular clinical trials and will have representations from the working group on pacing and electrophysiology of the Danish Society of Cardiology, as well as representatives from Danish Stroke Neurologists. The main focus of the SC will be on the medical, ethical and scientific integrity of the study and on its timely completion. The SC will consider sample size re-examination in the eventuality at the observed, blinded pooled event rate for the primary endpoint falls below the assumptions from the design stage. SC members may be investigators in the study. To facilitate the communication of results from the study, a publication committee will be formed from the SC at an appropriate time, consisting of members of the SC and of others, who have contributed significantly to the study.

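### The Steering Committee that adapts sample size and follow-up may also see results by group, so blinding of the adaptation is not assured and the 5% level is not protected

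*Protocol*

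**What the plan says.** **Basis of adaptation.** Section 10.7.1 has the SC reconsider sample size if the "observed, blinded pooled event rate for the primary endpoint falls below the assumptions" made at the design stage. Sections 3.5 and 10.4 likewise refer to an event rate or a number of primary endpoints.

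**Access.** Section 10.5 first gives the SC individual treatment assignments on request, without naming a purpose. It then states: "Un-blinded (presented as group A and B) results, including aggregate and subject level data, can be presented to the SC for safety data reviews".

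**Powers of the same committee.**
- Section 10.4: the SC decides whether the study continues as planned once about one third of subjects have a year of follow-up. It adds: "The SC has the right to increase sample size or prolong follow-up if needed".
- Section 3.5: the SC may recommend longer follow-up or a changed sample size.
- Section 13.1: the SC may terminate the study; no criteria are given.
- Section 10.7.1: "SC members may be investigators in the study".

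**End of study.** Section 10.1 expects the trial to end at 279 strokes or when 6,000 subjects have at least 36 months of follow-up. Section 10.3 adjusts follow-up to reach the event number.

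**The concern.** A blinded adaptation is blinded only if those who decide cannot see outcome by arm. Here one committee holds both the decision and the access.

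The safety purpose attached to by-group results does not keep efficacy out. Section 9.1.1 lists stroke and peripheral emboli among adverse events, and Appendix C sends the SC a summary of serious events every six months. Appendix C does not say that this summary is split by group, but section 10.5 would allow a split. Labels A and B conceal little when one group is three times the size of the other.

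If the SC had seen strokes by arm and could then end at 36 months or continue to 279 events, a reader of the final result could not exclude that the end date was chosen with knowledge of the treatment difference. A later analysis plan cannot restore blinding once such access has been used.

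**Working it through.** **1. The plan's event number.** Section 10.3: "We thus expect the overall hazard ratio to be 0.65", and "with a 2-sided α-level of 0.05 and a power of 80% in a 1:3 intervention:control-randomized population, we will need 279 primary events". Freedman's formula with k = 1/3 (intervention to control):

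d = (1.960 + 0.842)² × (1 + k·HR)² / [k(1 − HR)²] = 7.849 × 1.2167² / (0.3333 × 0.1225) = 284.5.

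This is within about 2% of 279. Continuity-corrected proportions at 1.0% and 0.65% per year give 280. The figure of 279 is therefore accepted. (Schoenfeld's formula gives 226.)

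**2. How far apart the two ends are.** Inputs from section 10.3: control rate 1% per year, HR 0.65, 4,500 and 1,500 subjects, no allowance for attrition.
- Events per year: 4,500 × 0.01 + 1,500 × 0.0065 = 54.75.
- At 3 years: 164. At 4 years: 219. Time to 279: 279 / 54.75 = 5.1 years.

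The 36-month end thus arrives with about 59% of the events of the other end (164/279), so choosing between them is a real decision under the protocol's own rates.

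**3. When the section 10.4 review falls.** Assume uniform recruitment over 1 or 2 years (section 10.3) and a pooled rate of 54.75/6,000 = 0.9125% per year.
- Recruitment over 1 year: one third recruited by month 4, review at month 16; 6,000 × (1.333 − 0.5) = 5,000 person-years, 46 events, 16% of 279.
- Recruitment over 2 years: one third recruited by month 8, review at month 20; 3,000 × 1.667² / 2 = 4,167 person-years, 38 events, 14% of 279.

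The review is therefore at about 15% of the events.

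**4. Type I error.** All figures are two-sided, under no treatment effect, with an unadjusted final test at |Z| > 1.96. For a choice between d1 and d2 events, Z1 and Z2 are bivariate normal with correlation √(d1/d2), and the error is P(|Z1| > 1.96 or |Z2| > 1.96). The three-point case was simulated. For the increase-only case, at information fraction t = 0.15, the final size n (in multiples of 279, from 1 to a cap of 1.5 or 2) is chosen to maximise P(|Zn| > 1.96 given z1), where Zn given z1 is normal with mean z1√(t/n) and variance 1 − t/n; the result is averaged over z1.

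| Behaviour of the SC | Type I error |
|---|---|
| Follow-up set from pooled counts only (Poisson simulation, rate 0.6% to 1.0% per year, follow-up 3 to 8 years) | 4.97% to 5.01% |
| Increase-only at about 15% of events, worst-case use of arm results | 5.3% to 5.4% |
| End at 215 or 279 (correlation √(215/279) = 0.878) | 7.2% |
| End at 164 or 279 (correlation 0.767) | 8.0% |
| End at 164, 219 or 279 | 9.2% |

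The 215-event point is illustrative and close to the 219 expected at 4 years. By symmetry half of each figure is false benefit: 3.6% against 2.5% in the 215 or 279 case. Stopping only for harm or futility adds nothing.

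**The case against.** A reader might infer that the adaptation is unblinded and that the trial therefore runs at a type I error of 7% to 9%. The documents do not support that. Section 10.5 is permissive, and it limits by-group results to safety reviews. Every stated trigger for adapting (sections 3.5, 10.3, 10.4 and 10.7.1) is an event rate or count. The protocol plans no significance test at 164, 215 or 219 events, and the one scheduled review comes early, where even the worst increase-only use of arm data costs 0.3 to 0.4 points. Under a rule that is really pooled there is no inflation.

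Nor would a by-group safety table be the primary endpoint itself. That endpoint is adjudicated, with blinding (section 10.7.2 and Appendix J), whereas adverse-event tables hold reported events. Investigators on the SC add little, since in an open-label trial they already know their own patients' arms. Any alpha adjustment might also stand in an analysis plan that is not at hand.

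All of this stands, and it limits the point to a missing separation. It does not remove it. The sentence on individual assignments has no safety limit, reported stroke is a close proxy for adjudicated stroke, and the passages giving access and powers set no barrier between the two.

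**Conclusion.** Sections 10.5 and 10.7.1 are at odds: one allows the SC to see outcome by arm, the other relies on its not doing so. Blinding of the adaptation is not assured, and the 5% level is not protected.

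The size is conditional. It is 5.0% if only pooled counts are used, 5.3% to 5.4% for an early increase-only decision informed by arm, and 7.2% to 9.2% if the end of study is chosen with knowledge of arm results. The upper figures assume that the SC ends the trial when the unadjusted test is significant and otherwise continues; they describe what the wording leaves open, not what the plan prescribes. They also assume the protocol's event rates without attrition. The weakness is worth correcting because the correction is cheap and cannot be made after the access has been used.

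**What to change.** - **Section 10.5:** delete SC access to individual assignments on request. Send by-group safety data, including all strokes and bleeds, to persons outside the SC who take no part in decisions on sample size, follow-up or efficacy stopping, and who report only a safety recommendation to the SC. Strokes and bleeds should stay together in that review: hemorrhagic stroke is part of the primary endpoint (Appendix F) and also a major bleed (Appendix J), so a rule that withheld endpoint components while keeping bleeding would contradict itself.
- **Sections 3.5, 10.4 and 10.7.1:** state that any change to sample size or follow-up uses pooled primary-event counts only, and that no SC member sees stroke or embolism by arm before database lock.
- **Section 10.1:** reconcile the two end-of-study conditions into one event-based rule consistent with section 10.3.

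The cost is protocol wording and a small review group outside the SC. The downside is that the SC loses direct sight of strokes by arm during the trial; review of those events by arm continues elsewhere.

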# 10.6 Planned Methods of Analysis:

# 10.6.1 General Approach/Considerations:

Baseline characteristics, demographics, pre-existing conditions, previous illnesses, and possible prior treatments will be summarized for each treatment group. Subjects disposition and reason for discontinuation will be summarized for each group. The primary and secondary efficacy endpoints are timed to event variables and survival techniques will be utilized to perform statistical estimation and hypothesis testing. Concomitant medications will be summarized for each treatment group and compared between groups to access their potential impact on the primary endpoint.

# 10.6.2 Analysis of Key Study Endpoints:

# 10.6.2.1 Primary Endpoint:

The principle analysis for the primary endpoints will employ the intend-to-treat principle, and use a survival analysis. To account for the competing risk of death, the cumulative incidences of the primary endpoint will estimated, plotted and group-wise compared in a multi-state fashion. A co-variate adjusted analysis of the combined primary endpoint using a cause-specific Cox proportional regression model will be performed as a supportive analysis. The hazard ratios and the corresponding 95% confidence intervals will be estimated. Subjects completing the study and not reaching the composite endpoint will be censored.

# 10.6.2.2 Secondary Endpoints:

See section 10.2.2.

For the time-to-event variables, analysis similar to the one employed for the primary endpoint will be used. The censoring mechanism will also be similar to the one used for the analysis of the primary endpoint. The secondary endpoints will be tested at a significance level of 0.05. Within the first two secondary endpoints the type 1 error rate associated with a multiplicity of comparisons will be controlled according to the Hochberg adjustment. The Quality of Life endpoint will be tested at the 5% significance level. Quality of Life score will be analysed as repeated measures analysis of covariance mixed effects model using baseline score as a covariate.

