# 10.2.2 Secondary Endpoints:

- Composite endpoint of time to adjudicated stroke, or systemic arterial embolism, or cardiovascular death
- Time to death by any cause
- Time to cardiovascular death
- Time to adjudicated ischemic stroke
- Time to adjudicated transitory ischaemic attack
- Time to diagnosis of atrial fibrillation
- · Time to diagnosis of atrial flutter

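### Section 10.6.2.2 states no link between secondary testing and the primary result and limits Hochberg to two of seven secondary endpoints, so error is controlled within the pair but not across the trial's claims

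*Protocol*

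**What the plan says.** The primary endpoint has its own level: section 10.3 sizes the trial "with a 2-sided α-level of 0.05 and a power of 80" per cent. For the secondary endpoints, section 10.6.2.2 gives three rules:

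- A general level for all of them: "The secondary endpoints will be tested at a significance level of 0.05".
- A multiplicity adjustment whose scope stops at two endpoints: "Within the first two secondary endpoints the type 1 error rate associated with a multiplicity of comparisons will be controlled according to the Hochberg adjustment".
- A separate test of Quality of Life, given its own 5%.

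Section 10.2.2 lists seven secondary endpoints. The first two, which form the Hochberg pair, are the composite of stroke, systemic embolism or cardiovascular death, and death from any cause. The remaining five are cardiovascular death, ischaemic stroke, TIA, AF ("Time to diagnosis of atrial fibrillation") and atrial flutter. Quality of Life is not among the seven; it appears with the supplementary endpoints in section 10.2.4.

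Neither the synopsis nor sections 10.2, 10.3 and 10.6 give a gate, a testing order, a split of alpha, or a statement that the unadjusted tests are exploratory.

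**The concern.** A Hochberg step signals that the first two secondary endpoints are meant to carry confirmatory weight. As written, the pair opens with a fresh 0.05 and nothing ties it to the primary. If the primary misses, the text does not prevent a significant composite or mortality result from being presented as error-controlled. That matters here because section 2.5.1 puts a lower death rate within the major hypothesis, as a secondary endpoint, and the expected results in section 1 speak of benefit through mortality or morbidity.

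Six further tests, five secondary endpoints and Quality of Life, run at 0.05 each with nothing to mark a significant result among them as descriptive.

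Time to AF diagnosis needs separate handling. Section 10.3 expects AF in 30% of participants under ILR monitoring, against 3% of controls diagnosed and started on anticoagulation. A difference there is close to built in. It reflects detection, and is neither evidence of benefit nor a false positive.

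**Working it through.** **Is there a plan figure to reproduce?** The protocol gives no error rate across endpoints. Its nearest figure is the 279 events of section 10.3. The Freedman formula with 1:3 allocation and hazard ratio 0.65 gives 7.849 × (1 + 0.65/3)² / [(1/3) × 0.35²] = 284.5 events, within about 2% of 279. Nothing below depends on it.

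**Inputs.** Primary at two-sided 0.05 (section 10.3). Hochberg at 0.05 on two endpoints, 0.05 on each of five others and 0.05 on Quality of Life (section 10.6.2.2, with the list in section 10.2.2). All nulls are taken as true. Correlations are not given, so a range is shown.

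**The pair.** With two independent tests, Hochberg makes a claim if both p-values are at most 0.05, or if the smaller is at most 0.025: 0.05² + 2 × 0.025 × 0.95 = 0.0025 + 0.0475 = 0.05. The pair therefore counts as one test at 0.05.

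**Independence.**

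- Primary or pair: 1 − 0.95² = 0.0975.
- Seven secondaries (pair + 5): 1 − 0.95⁶ = 0.265.
- Seven secondaries plus Quality of Life: 1 − 0.95⁷ = 0.302.
- The same without AF diagnosis (pair + 4 + Quality of Life): 1 − 0.95⁶ = 0.265.
- Primary plus everything: 1 − 0.95⁸ = 0.337.

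**Positive correlation.** The endpoints overlap: cardiovascular death sits inside both members of the pair, and ischaemic stroke sits inside the composite. Simulation with 500,000 replicates, two-sided tests and a common correlation gives the last two columns. The first column is from the formulas above, except the conditional row: under independence a failed primary does not change the secondary rate.

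| Chance of at least one false claim | Independent | Correlation 0.5 | Correlation 0.8 |
|---|---|---|---|
| Hochberg pair alone | 0.050 | 0.048 | 0.044 |
| Primary or pair | 0.0975 | 0.089 | 0.072 |
| Seven secondaries | 0.265 | 0.204 | 0.133 |
| Seven secondaries + Quality of Life | 0.302 | 0.227 | 0.144 |
| Primary + seven + Quality of Life | 0.337 | 0.247 | 0.153 |
| Seven secondaries, given a non-significant primary | 0.265 | 0.186 | 0.099 |

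Only the pair alone stays at or below 0.05.

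**Would a wider Hochberg do instead?** Hochberg over all seven without a gate holds the secondary family at 0.049 (independent) and 0.041 (correlation 0.5). Taken with the primary, the rate is still 0.096 and 0.081. Trial-level control needs a gate or an alpha split.

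**Identity of the pair.** Section 10.2.2 builds the first secondary endpoint with cardiovascular death. The synopsis endpoint list builds it with death unqualified, and the secondary objectives in the synopsis and section 1 say mortality. The pair is therefore not uniquely identified.

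**The case against.** The strongest reply is that section 10.6.2.2 promises control only within the first two secondary endpoints, and Hochberg delivers it. That stands. A reader might infer that the section offers a 5% family-wise rate for all secondary endpoints and breaks it. It does not: the 0.05 for the other tests is a level per test. Nor is the plan without error control, since the pair is controlled and no secondary result spends or alters the primary's 0.05.

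A second reply is that the analysis plan, not shown, may add a gate. A gate would not contradict any sentence in section 10.6.2.2. So the reading that the protocol authorises secondary claims whatever the primary shows goes too far; the text is silent on the point. The reply does not dispose of the rest. The protocol itself fixes the level, the scope of Hochberg and a further 5% for Quality of Life, so a plan that only follows it inherits the gap.

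A third reply is that 30% exaggerates. That is fair. It assumes independence, which the overlap between endpoints makes implausible, and it counts AF diagnosis as a true null when the design expects a difference. It is the upper end of a range. Whether AF diagnosis is informative about benefit is a matter of interpretation and is not itself a multiplicity error.

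Finally, a gate is one choice among several; an alpha split, or labelling all secondary endpoints supportive, would also be coherent.

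**Conclusion.** The point holds as a gap in the stated testing rule. It does not threaten the primary conclusion. With all nulls true, the primary and the pair together carry a false-claim rate of about 7% (correlation 0.8) to 9.75% (independence). The seven secondaries plus Quality of Life carry about 14% to 30%, or at most about 26% without AF diagnosis. The common correlations are assumed, so the figures show a range and are not estimates for this trial. That no gate exists is read from the absence of any stated condition in the protocol. The conflicting definitions of the composite are a separate matter of text and need no assumption.

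**What to change.** Amend section 10.6.2.2 with two sentences:

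1. The Hochberg pair is tested only if the primary endpoint is significant at two-sided 0.05.
2. The remaining five secondary endpoints and Quality of Life are reported with 95% confidence intervals as descriptive, without significance claims.

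Every confirmatory claim then requires a significant primary, so with all nulls true the chance of any false claim is 0.05.

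In the same edit, reconcile the composite that opens the pair (cardiovascular death in section 10.2.2, any death in the synopsis), so that the two gated endpoints are identified without doubt.

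The change needs no extra data or subjects. Its price is that no confirmatory secondary claim, including one on mortality, is possible if the primary fails. If the sponsor will not accept that, a stated split of alpha between the primary and the pair would also control the overall rate, at the cost of a stricter level for the primary than section 10.3 assumes.

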#### 10.6.2.3 Safety Endpoint:

AEs: Subjects incidence rates of all AEs will be tabulated by system class, preferred term, severity, and relationship to investigational product. Tables and/or narratives of "on-study" death, and serious and significant AEs, including those causing early withdrawal, will also be provided.

Complications from ILR implantation will be asked for and registered at all visits.

# 10.7 Study Oversight:

# 10.7.1 Steering Committee:

A SC comprising experts in the cardiovascular field will provide oversight and advice to ensure the most safe and efficient conduct and execution of the trial. The SC will consist of external physicians with experience and expertise in the design and conduct of cardiovascular clinical trials and will have representations from the working group on pacing and electrophysiology of the Danish Society of Cardiology, as well as representatives from Danish Stroke Neurologists. The main focus of the SC will be on the medical, ethical and scientific integrity of the study and on its timely completion. The SC will consider sample size re-examination in the eventuality at the observed, blinded pooled event rate for the primary endpoint falls below the assumptions from the design stage. SC members may be investigators in the study. To facilitate the communication of results from the study, a publication committee will be formed from the SC at an appropriate time, consisting of members of the SC and of others, who have contributed significantly to the study.

# 10.7.2 Endpoint Committee:

An endpoint committee (EC) will be formed prior to study commencement to adjudicate the primary endpoints in a blinded fashion (see Appendix B and F). A neurologist and a cardiologist are appointed in the EC.

With respect to correct classification of recorded AF events an "AF adjudication committee" will be established among the cardiologists in the SC. "The AF adjudication committee" will be composed of two cardiologist (rotation among SC members will occur). If these two cardiologists disagree a third cardiologist will be involved for final adjudication of AF.

